- g: Centralized skin assessments using standardized photography will be conducted by a reviewing dermatologist. These assessments will specifically include evaluation of any areas of depigmentation or any rash. Additional UNS dermatological assessments should be conducted in response to any dermatological AEs of concern (eg, depigmentation, rash, herpetic lesion).
- h: Examples of neurological signs that may indicate new central nervous system pathology that may need further investigation include (but not limited to) visual disturbance, dysarthria, dysphasia, muscle strength, limb weakness, hyperflexia, paraparesis, micturition difficulty or urgency or incontinence, ataxia, neuropsychiatric or cognitive decline in excess of expectations based on the subject's recent history. The Brief Smell Identification Test (Sensonics Inc.) will be administered at the same visits and serves as part of the neurologic examination. (revised per Amendment 04)
- i: If the subject experiences visual disturbances during the course of the study, the subject will be referred to a specialist for a further ophthalmic examination, which should include fundoscopy to look at the optic disc, macula and the rest of the retina as well as an assessment of visual acuity and visual fields
- j: Please refer to [Section 9.4.7](#), which details prohibited and permitted medications in the study and associated timeframes.
- k: 12-lead standard ECGs will be recorded in triplicate (1 minute apart).

Footnotes for Table 7

- l: Lymphocyte subsets will include but are not limited to the following cell surface marker assessments: CD4 [T helper cells], CD8 [cytotoxic T cells], CD19 [B cells], CD16/CD56 [NK cells] and CD14 [macrophages] and total lymphocytes. Regulatory T cells will also be measured. Viability staining may also be employed. Whenever unscheduled lymphocyte subset tests are performed or whenever scheduled lymphocyte subsets are repeated, a Complete Blood Count, with differentials, must also be performed along with assessment of AEs. (revised per Amendments 02 and 04)
- m: Igs to be analyzed include IgG, IgA, and IgM.
- n: An additional assessment is required if a negative screening pregnancy test was obtained more than 72 hours before the first dose of study drug.
- o: Blood samples will be collected and stored. These samples may be used for exploratory biomarker analyses, or in the event that the subject develops a TEAE that warrant further investigation (eg, treatment-emergent infection), these samples may be tested to determine whether the subject already had prior exposure to any suspected infective agents.
- p: These assessments are to be completed in the morning whenever possible, or consistently at the same time of day. These assessments should be completed before more invasive assessments or procedures (eg, physical examination, ECG, blood draws). The order of assessments will be: MMSE, CDR, ADAS-cog14, FAQ, ISLT (immediate recall), CBB, and ISLT (delayed recall). At visits where the CDR or FAQ are conducted, the investigator will determine whether the informant must attend in person or whether telephone contact will be suitable, and will base this determination upon the functional ability of the subject among other factors.
- q: Safety MRIs will be acquired using a standardized procedure that will include gradient echo, long tau inversion recovery, and diffusion-weighted imaging sequence images in MRI will be read by an approved central reader. MRI imaging will be conducted on separate days from the scheduled visits. MRI imaging should be conducted within the 7 days before Visits 14, 16, 18, and 20. In the event of an Unscheduled Visit, the investigator in consultation with the sponsor will determine whether or not a safety MRI should be conducted. If an ED Visit takes place, an MRI is to be conducted if not already performed during the preceding 90 days. A volumetric MRI sequence will be collected in all subjects immediately following all safety MRI assessments. (revised per Amendment 01)
- r: PET scanning will be performed with a locally approved amyloid β imaging agent, eg, Amyvid, if available or an agent under clinical investigation if no agents are approved locally; the imaging agent must remain unchanged for an individual subject throughout the study. A PET scan will only be performed at an ED Visit if the subject has been treated with study drug for at least 39 weeks. A PET scan will only be performed at Visit 18 or ED if the subject has a valid Screening PET scan for the purposes of longitudinal analyses; subjects who were determined to be eligible for the study on the basis of an historical PET scan will not have a PET scan performed at Visit 18 or ED (revised per Amendment 02)
- s: Site staff will contact the subject or the caregiver or informant the day before the PK blood sampling to provide instructions that subjects must not take their study drug at home on the day of the PK blood sampling. During this telephone contact with the subject or the caregiver or informant, the site staff should document the time that the subject took their study drug that day, ie, the day before the PK blood sampling.
- t: Two plasma PK samples will be obtained: one at predose (trough) and another 1 to 6 hours postdose at Visit 5, Visit 11, Visit 14, and Visit 16 and 4 to 8 hours postdose at Visit 7 and Visit 18 (or ED). Therefore, subjects or their caregivers or informants must be instructed not to take their study drug at home on the day the PK sampling is performed. Instead, subjects will take the study drug at the clinic after collection of the predose PK sample. At Visit 7 and Visit 18 (or ED) the PK blood sample should be collected shortly before or shortly after completing the LP. If at an ED Visit, the subject has already stopped study drug, then no dosing will take place, but the trough PK sample will still be collected, followed by LP at approximately the same time as at previous visits. A second PK blood sample will be collected as close as possible to the LP, either shortly before or shortly after the LP. (revised per Amendment 01)
- u: PD and exploratory biomarker blood samples should be collected at fasting or at least 2 hours after the most recent meal and, as far as is feasible, samples should be taken at the same time of day. At Visits 5, 11, 14, and 16 the PD blood samples should be collected predose.
- v: For subjects who consent to CSF sample collection: Postrandomization CSF sample collection is scheduled at Visit 7 (or later postrandomization timepoint) and Visit 18/ED. If a postrandomization CSF sample is collected later than Visit 7, time-matched plasma PK samples are also required (see Footnote t). All visits at which CSF samples are scheduled to be taken also include blood PK and PD assessments and so the subject will be dosed at the clinic on these days. The timing of the Baseline LP needs to be

Footnotes for Table 7

scheduled carefully such that subsequent LPs (Visit 7 [or later postrandomization timepoint] and Visit 18) can be performed between 4 and 8 hours postdose and at a similar time of day (± 1 hour) for each individual subject. The CSF sample will be taken with the subject fasting (preferred) or at least 2 hours after the most recent meal. A gravity drip collection method must be used. If the LP and the cognitive tests are performed on the same day, the LP must be performed after the cognitive tests have been completed and the subject should rest and drink some fluid to hydrate before the LP. Subjects will be encouraged to stay at the site after completion of LP for medical observation. The CSF sample will not be taken at the ED Visit if this visit occurs within 3 months of a previous CSF sample. If at an ED Visit, the subject has already stopped study drug, then no dosing will take place, but the CSF sample will still be collected unless it was already collected within the past 3 months. . Subjects who initially consented to CSF collection and provided a baseline CSF sample but did not provide a postrandomization sample will be approached to consider reconsenting to postrandomization CSF sample collection even if they are beyond Week 5 (Visit 7); however, subject consent to this procedure is optional for these subjects. (revised per Amendments 01, 02, and 04)

- w: Subjects reporting AEs relating to abnormal dreams, nightmares, or sleep terror will be questioned on the frequency and impact of these events.
- x: The first dose of study drug will be given to the subject at the study site and the subject will be encouraged to stay at the site for an appropriate period of time as determined by the PI or Safety Physician for postdose medical observation. (revised per Amendment 02)

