9.1.2 Randomization Phase

Subjects who complete the Baseline Visit assessments, and are eligible based on the inclusion and exclusion criteria (see [Section 9.3.1](#) and [Section 9.3.2](#)), will begin the Randomization Phase no more than 10 days after completion of the Baseline Visit assessments and confirmation of the eligibility of the subject based on the results of all the Baseline Visit assessments (revised per Amendment 02).

The Randomization Phase will consist of a Treatment Period of 78 weeks duration and a Follow-Up Period of 12 weeks after the last dose of study drug.

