9.1.2.3 Follow-Up Period

All subjects, regardless of whether they complete all 18 months of treatment or discontinue study drug prematurely, will complete 4 post-treatment Follow-Up Visits: 2, 4, 8, and 12 weeks after the last dose of study drug. If clinically indicated, more frequent safety assessments can be conducted as part of unscheduled visits during the post-treatment Follow-Up Period. (revised per Amendment 04)

The end of the study will be defined as the date of the clinical database lock (ie, when all study data are collected and data validation is completed).

As required by some regulatory agencies, the following estimates are provided:

- The study will begin in Nov 2014 and is projected to end by Oct 2019 (end date will depend on actual recruitment rate).
- The maximum estimated period for each subject on study is anticipated to be approximately 2 years.

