- p: A blood sample will be collected at Baseline and stored. This sample may be used for exploratory biomarkers associated with study drug or disease, or in the event that the subject develops TEAEs that warrant further investigation (eg, treatment-emergent infection), these samples may be tested to determine whether the subject already had prior exposure to any suspected infective agents.
- q: Viral characterization will include testing for previous exposure to CMV, HSV1, HSV2, etc.
- r: Centralized skin assessments using standardized photography will be conducted by a reviewing dermatologist. These assessments will specifically include evaluation of any areas of depigmentation or any rash. See [Section 9.5.1.5.8](#) for further details.
- s: To be performed by either a neurologist or a physician with comparable training and experience in undertaking neurologic examinations. [Section 9.5.1.5.9](#) details what is included in the neurological examination. The Brief Smell Identification Test (Sensonics Inc.) will be administered at the same visits and serves as part of the neurological examination. (revised per Amendment 04)
- t: An ophthalmic examination will be conducted at Visit 2 unless the subject has had a comprehensive eye exam within the past 12 months, from which a report is available. The ophthalmic examination should include funduscopy to look at the optic disc, macula and the rest of the retina as well as an assessment of visual acuity and visual fields.

Table 7 Schedule of Procedures/Assessments in Study 202: Randomization Phase (Visit 3 through Visit 20)

| Phase Period | Randomization | | | | | | | | | | | | | | | | | | | | UNS Visit ^d | |
|--|----------------|---|----|----|----|----|----|----|----|-----|-----|-----|-----|-----|-----|-----|-----------------|-----------|-----------------|-----|---------------------------|----------------|
| | Treatment | | | | | | | | | | | | | | | | | Follow-Up | | | | |
| Visit ^a | 3 | 4 | 5 | 6 | 7 | 8 | 9 | 10 | 11 | 12 | 13 | 14 | 15 | 16 | 17 | 18 | ED ^b | W2 | 19 ^c | W8 | 20 ^c | |
| Day | 1 | 8 | 15 | 22 | 29 | 43 | 57 | 71 | 85 | 113 | 141 | 183 | 274 | 365 | 456 | 547 | | 561 | 575 | 589 | 631 | |
| Week | 1 | 2 | 3 | 4 | 5 | 7 | 9 | 11 | 13 | 17 | 21 | 27 | 40 | 53 | 66 | 79 | | 81 | 83 | 87 | 91 | |
| Weeks elapsed since first dose | 0 | 1 | 2 | 3 | 4 | 6 | 8 | 10 | 12 | 16 | 20 | 26 | 39 | 52 | 65 | 78 | | 80 | 82 | 86 | 90 | |

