ADAS-cog₁₄ = Alzheimer's Disease Assessment Scale - Cognitive subscale (14 items), CBB = CogState Brief Battery, CBP = childbearing potential, CDR = Clinical Dementia Rating scale, CSF = cerebrospinal fluid, C-SSRS = Columbia Suicide Severity Rating Scale, ECG = electrocardiogram, ED = Early Discontinuation, FAQ = Functional Assessment Questionnaire (also known as the Functional Activities Questionnaire), Ig = immunoglobulin, ISLT = International Shopping List Task, LP = lumbar puncture, MMSE = Mini Mental State Examination, MRI = magnetic resonance imaging, PBMC = peripheral blood mononuclear cell, PD = pharmacodynamics, PET = positron emission tomography, PK = pharmacokinetics, UNS = unscheduled, W2 = new Week 2 follow-up visit, W8 = new Week 8 follow-up visit. (revised per Amendment 04)

- a: Visit 3 should be conducted no more than 10 days after completion of the Baseline visit (Visit 2) assessments and confirmation of eligibility to continue in the study, unless additional time is required to take Exclusion Criterion #20 into account. (revised per Amendment 02) A window of ± 3 days will be permitted for Visit 4 to 14 inclusive. A window of ± 10 days will be permitted for Visit 15 to 18 inclusive. A window of ± 3 days will be permitted for the Follow-Up Visits. If use is made of the permitted visit windows, every effort should be made to bring the subject back in line with the "weeks elapsed since first dose" at subsequent visits.

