- b: Subjects who discontinue taking study drug prematurely for any reason will undergo an ED Visit within 7 days of their last dose of study drug. In addition, Follow-Up Visits will be scheduled 2, 4, 8, and 12 weeks after the last dose of study drug (Visit W2, 19, W8, and Visit 20, respectively). Subjects who discontinue study drug prematurely will also be scheduled to return to the study site for each scheduled visit when clinical efficacy assessments are to be conducted (ie. at Visits 11, 14, 15, 16, 17, and 18, if these visits have not already been performed). At these visits, only clinical efficacy assessments (MMSE, CDR, ADAS-cog₁₄, FAQ, CBB, and ISLT) will be conducted. Regularly scheduled clinical efficacy visits do not need to be attended if they fall within 8 days (visit window) after the Early Discontinuation Visit or within ± 8 days of Follow-Up Visit 19 of Visit 20). Subjects who discontinue early from study drug are considered on study as long as they return for their regularly scheduled clinical efficacy visits as outlined above. (revised per Amendment 04)
- c: All subjects, regardless of whether they complete all 18 months of treatment or discontinue study drug prematurely, will complete 4 post-treatment Follow-Up visits; 2, 4, 8, and 12 weeks after the last dose of study drug (Visits W2, 19, W8, and 20, respectively). If clinically indicated, more frequent safety assessments can be made as UNS assessments or visits during the post-treatment Follow-Up period. (revised per Amendment 04)
- d: Unscheduled visits may be conducted at any time that safety or safety MRI data indicate per protocol or as clinically indicated in the judgment of the investigator. Note that not all assessments indicated under UNS Visits need be conducted – actual assessments needed will be determined by the investigator and will be based on the specific visit needs.
- e: Only if clinically significant abnormalities are found at Visit 19 and the investigator considers it necessary to repeat at Visit 20. Clinical biochemistry, urinalysis, CBC, lymphocyte subsets and Igs should always be performed at Visit 20, regardless of clinical significance at the previous Follow-Up visit. (revised per Amendments 02 and 04)
- f: Measurements of body temperature and sitting blood pressure and heart rate will be obtained.

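### Table 7 gives the W8 follow-up visit a Day number that is 6 weeks after the last dose, while its own week rows, its label, its footnotes and Section 9.1.2.3 give 8 weeks

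*Protocol*

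**What the plan says.** Section 9.1.2 fixes the time frame: "The Randomization Phase will consist of a Treatment Period of 78 weeks duration and a Follow-Up Period of 12 weeks after the last dose". Section 9.1.2.3 says that all subjects "will complete 4 post-treatment Follow-Up Visits: 2, 4, 8, and 12 weeks after the last dose of study drug".

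Table 7 in Section 9.5.2.1 turns this into a calendar with three rows counted from the first dose: Day, Week, and weeks elapsed. Visit 18, the end of treatment, is Day 547, Week 79, 78 weeks elapsed. For W2, 19, W8 and 20 the Day row reads "561 | 575 | 589 | 631". The Week row gives 81, 83, 87 and 91, and the weeks-elapsed row gives 80, 82, 86 and 90. The header is printed twice with the same values.

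The abbreviations under the table define the visit: "W8 = new Week 8 follow-up visit". Footnote c places the visits at "2, 4, 8, and 12 weeks after the last dose of study drug (Visits W2, 19, W8, and 20, respectively", and footnote b gives the same mapping for early discontinuers. On timing, footnote a states that a window of plus or minus "3 days will be permitted for the Follow-Up Visits".

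**The concern.** A schedule table is an operative part of a protocol, from which sites and visit-scheduling systems can be expected to work. In the W8 column the Day entry and the two week entries point to dates two weeks apart, and the permitted window is too narrow to cover both. A visit on target under one row is a deviation under the other.

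W8 exists for off-drug safety follow-up. Complete blood count, lymphocyte subsets, immunoglobulins and adverse events are due then. Immunological and hematological safety is named in the second primary objective (Section 8.1). Time off drug matters for these measures: Section 7.1 reports that lymphocyte effects in the multiple-dose study resolved gradually between 6 and 21 days after the last dose. Section 9.7.1.8.3 summarizes laboratory values by visit. If some sites followed the Day row and others the week rows, the W8 summary could combine values taken about 6 and about 8 weeks off drug. With about 125 sites planned for Stage B (Section 6), uniform reading should not be left to chance.

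**Working it through.** **Inputs.** The Day, Week and weeks-elapsed rows of Table 7 for all 20 dated visits (Visits 3 to 18, W2, 19, W8, 20); the last dose at Visit 18 on Day 547; the follow-up window of 3 days either side from footnote a.

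**Rules that the table follows.** Day = 7 × weeks elapsed + 1. Week = weeks elapsed + 1. Weeks after last dose = (Day − 547) / 7.

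**Reproducing the printed days.** All 16 treatment-period visits fit both rules, for example Visit 14: 7 × 26 + 1 = 183, and Visit 17: 7 × 65 + 1 = 456. From Visit 18 on:

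| Visit | Weeks elapsed | Week printed | 7 × elapsed + 1 | Day printed | (Day printed − 547) / 7 |
|---|---|---|---|---|---|
| 18 | 78 | 79 | 547 | 547 | 0 |
| W2 | 80 | 81 | 561 | 561 | 2.0 |
| 19 | 82 | 83 | 575 | 575 | 4.0 |
| W8 | 86 | 87 | **603** | **589** | **6.0** |
| 20 | 90 | 91 | 631 | 631 | 12.0 |

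Nineteen of the 20 dated visits reproduce exactly; W8 is the only mismatch.

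**What Day 589 corresponds to.** (589 − 1) / 7 = 84 weeks elapsed, hence Week 85, against the printed 86 and 87. The week rows give 86 − 78 = 8 weeks after the last dose; the Day row gives 6.

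**Size of the gap.** 603 − 589 = 14 days.

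**Does the window bridge it?** From the Day row: 589 ± 3 = Days 586 to 592. From the week rows: 603 ± 3 = Days 600 to 606. The two ranges do not overlap.

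**Could it be a reading artefact?** Unlikely. The value is 589 in both printings of the header, and the neighbouring columns line up. A rounding or day-0 versus day-1 convention would not shift a single column by 14 days.

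**The case against.** The strongest reply is that this is a slip in one cell which the protocol largely resolves for itself. Two rows of the same column, the visit's label, footnotes b and c, and the repeated text on early discontinuation and follow-up all agree on 8 weeks. Footnote a also tells sites that use the visit windows to bring subjects back to the weeks-elapsed row, not the Day row. Much of this stands. It makes a uniform 8-week reading the likelier outcome, and it means that the document does not offer two schedules of equal standing. It does not make the printed Day harmless, because a site or system that takes target dates from the Day row would still land outside the window set by the week rows.

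A reader might infer that the 8-week data of every subject are compromised. The documents do not support that. Follow-up visits are counted from each subject's own last dose, so the fixed Day number fits only those who complete 78 weeks. Whether any site or system follows the Day row cannot be known from the protocol, since the visit-scheduling build is not shown. Mixed time points are therefore a possibility and not an established result.

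A reader might also infer that the efficacy analysis or an interim decision is at risk. It is not: Table 7 schedules no cognitive or functional assessment at W8. The follow-up points at 2, 4 and 12 weeks are consistent, and footnote e requires the blood count, subsets and immunoglobulins again at Visit 20 in all cases.

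**Conclusion.** The inconsistency is real and lies within the current table. For subjects who complete 78 weeks, the Day row and the two week rows of the W8 column differ by 14 days against a window of 3 days either side, and no date meets both. The consequence is limited to the timing of one of four post-treatment safety visits and, possibly, to the W8 entries of the descriptive by-visit safety summaries.

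The 6-week figure assumes a last dose on Day 547. Footnote a allows Visit 18 to move by 10 days either way. With a last dose between Day 537 and Day 557, Day 589 falls 589 − 537 = 52 to 589 − 557 = 32 days later, short of 8 × 7 = 56 days throughout. The 14-day difference between the rows does not depend on this, because both count from the first dose.

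Day 603 is only what the table's other rows imply. Which entry expresses the intended schedule is for the sponsor to confirm.

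**What to change.** Reconcile the Day, Week and weeks-elapsed entries of the W8 column, in both printings of the Table 7 header, with footnotes b and c and Section 9.1.2.3, so that one target date applies. Then check that the visit-scheduling system and any analysis windows for follow-up visits use that same target. If any subject has already reached W8, tabulate the actual days since last dose so that any off-target visits can be seen.

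The cost is a correction to one column of a table and a check of the matching scheduling entry. No sample size, endpoint or analysis method changes.

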9.5.2.2 Description of Procedures/Assessments Schedule

Please refer to [Table 6](#) and [Table 7](#) for the timings of the procedures and assessments to be performed during the study. Screening assessments will be organized into 4 tiers (see [Table 6](#), [Section 9.5.2](#), and [Figure 2](#)).

See [Section 9.5](#) for a full description of the procedures and assessments to be performed during this study.

[Table 8](#) presents the number of blood and CSF samples, and the total volume of blood and CSF that will be collected throughout the study. Additional samples may be taken at the discretion of the investigator if the results of any tests fall outside reference ranges or if clinical symptoms necessitate testing to ensure subject safety.

Table 8 Summary of Blood and CSF Sample Volumes

| Assessment | Total number of collection time points | Number of time points x volume per collection (mL whole blood or CSF) | | Total volume (mL whole blood or CSF) |
|--|--|---|---------------------------------|--------------------------------------|
| | | Screening and Baseline Periods | Treatment and Follow-Up Periods | |
| Blood | | | | |
| Chemistry | 12 | 2 x 2 mL | 10 x 2 mL | 24 mL |
| Hematology | 20 | 2 x 5 mL | 18 x 5 mL | 100 mL |
| Lymphocyte subset analyses ^a | 20 | 2 x 4 mL | 18 x 4 mL | 80 mL |
| PBMC | 4 | 1 x 16 mL | 3 x 16 mL | 64 mL |
| IgA, IgM, IgG | 10 | 2 x 2 mL | 8 x 2 mL | 20 mL |
| PT, PTT for INR | 2 | 2 x 3 mL | None | 6 mL |
| Thyroid function tests (thyroid stimulating hormone, free triiodothyronine and free thyroxine) | 1 | 1 x 3 mL | None | 3 mL |
| Viral screen (Hepatitis B and C) | 1 | 1 x 4 mL | None | 4 mL |
| Viral characterization | 1 | 1 x 4 mL | None | 4 mL |
| Vitamin B12 | 1 | 1 x 2 mL | None | 2 mL |
| Serum pregnancy test | 1 | 1 x 2 mL | None | 2 mL |
| Tuberculosis (interferon-gamma release assays) | 1 | 1 x 3 mL | None | 3 mL |
| Sample for immune status | 8 | 1 x 4 mL | 7 x 4 mL | 32 mL |
| PD sample | 9 | 1 x 4 mL | 8 x 4 mL | 36 mL |
| PK analysis | 7 | 1 x 3 mL | 6 x 6 mL | 39 mL |
| Pharmacogenetic sample | 1 | 1 x 3 mL | None | 3 mL |
| All blood samples, total volume whole blood collected | | 80 mL | 342 mL | 422 mL |
| CSF (For subjects who consent to CSF sample collection) (revised per Amendment 02) | | | | |
| PD and PK samples | 3 | 1 x 12 mL | 2 x 12 mL | 36 mL |

CSF = cerebrospinal fluid, Ig = immunoglobulin, INR = International Normalized Ratio, PBMC = peripheral blood mononuclear cell, PD = pharmacodynamics, PK = pharmacokinetic, PT = prothrombin time, PTT = partial thromboplastin time.

^a: Whenever unscheduled lymphocyte subset tests are performed or whenever scheduled lymphocyte subsets are repeated, a CBC with differentials must also be performed. Therefore, for each unscheduled or repeat test, an additional 9 mL will be collected (5 mL for hematology and 4 mL for lymphocyte subset analyses)
(Table 8 revised per Amendment 04)

